- d Participants should be supine and rested for at least 5 minutes before the ECG is recorded.
- e A urine pregnancy test will be performed and results determined locally (Section 8.3.2).
- f Urine drug and breath alcohol testing will be performed and results determined locally. Breathalyzer and COVID-19 test will be performed only on dosing days. (Section 8.3.3)
- g A result of "severe depression" on PHQ-8 will exclude the participant from the study.
- h Includes heart rate, systolic and diastolic blood pressure preferably with an automated device. Participants should be supine and rested for at least 5 minutes in a quiet setting before testing.
- i PI-NRS pain diary is to be completed daily, by the participant and checked for completeness by study site staff at each on-site visit indicated (Section 8.2.1.1).
- i All AEs and SAEs are to be recorded at the times indicated regardless off attribution.
- k Medical occurrences that begin before Baseline but after obtaining informed consent will be recorded as medical history, not as AEs.
- Wear wrist actigraph Day 1 to 14 and Day 50 to 64
- m To be performed prior to and approximately 7 hours after dosing
- n To be performed approximately 7 hours after dosing.
- o Qualitative written assessment is to be completed at Visit 14 only.

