## 2.2. Background

Nonclinical in vivo and in vitro studies of psilocybin found via literature searches demonstrate that when administered orally to rats psilocybin is rapidly dephosphorylated to psilocin in the intestinal mucosa by alkaline phosphatase and a nonspecific esterase, with approximately 50% of the total volume of psilocin absorbed from the digestive tract (Kalberer 1962). Maximum plasma levels are achieved after approximately 90 minutes (Chen 2011). When administered systemically (i.e., bypassing the gut), initial psilocybin metabolism is performed by tissue phosphatases, with in vitro studies indicating the kidneys as being among the most active metabolic organs (Horita 1961). Across species tested, the highest levels of psilocin were found in the neocortex, hippocampus, and thalamus (Hopf 1974).

Recent clinical studies using pharmaceutical-grade oral psilocybin under controlled conditions have been performed in healthy volunteers and various subpopulations to characterize the safety profile and evaluate the biological response (Tryp-8802 IB). The clinical studies presented similar safety profiles, with both psychological and physical AEs reported. During dose sessions, the most common adverse psychological events included anxiety, negative emotional states and paranoid/delusional thinking, and the most common physical effects were increased BP and HR, mild nausea, and mild headache.

Preliminary efficacy of psilocybin in clinical studies showed an improvement in symptomatic response in indications including substance use disorder, treatment resistant depression, and anxiety. Overall, psilocybin has been well tolerated at the doses examined in the clinical studies.

A detailed description of the chemistry, pharmacology, efficacy, and safety of TRP-8802 is provided in the current Tryp-8802 IB.

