## 8.2.2.3. Questionnaires and Forms Utilized During Dosing Sessions

- The Mystical Experience Questionnaire (MEQ30) has been widely used to assess the mystical experiences occasioned by psychedelics (Barrett 2015; MacLean 2011). This 30-item scale includes questions that assess mystical experiences, positive mood, transcendence of time and space, and ineffability.
- The Challenging Experience Questionnaire (CEQ27) assesses challenging experiences and has been frequently used in studies with psychedelics, including psilocybin.
   Questions assess the difficulty, meaningfulness, spiritual significance, and change in well-being attributed to the psychedelic experience (Barrett 2016).
- The Psychological Insight Questionnaire is a 23-item questionnaire that assesses insights into avoidance and maladaptive patterns; and goals and adaptive patterns (Davis 2021b).
- The Monitor Rating Form is used by the therapists present during the dosing session to provide ratings at different time points, including during/within the dosing session, the day after the dosing session, and at follow-up (i.e., monitor rating of enduring effects).

[figure not shown]
CONFIDENTIAL 43 27 February, 2024

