# 8.4. Adverse Events, Serious Adverse Events, and Other Safety Reporting

The definitions of AEs and SAEs can be found in Appendix 2, Section 10.2.1 and Section 10.2.2, respectively. Adverse event grading will be performed using the Toxicity Grading Scale for Healthy Adult and Adolescent Volunteers Enrolled in Preventive Vaccine Clinical Trials (US FDA Guidance for Industry 2007).

The investigator and any qualified designees are responsible for detecting, documenting, and recording events that meet the definition of an AE or SAE and remain responsible for following AEs that are serious, considered related to the study intervention or study procedures, or that caused the participant to discontinue the study (Section 7). During dosing sessions, manifestations of the psychedelic experience will not be recorded as AEs unless judged by the therapists to exceed the intensity and/or duration of expected reactions.

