# 8.5. Clinical Safety and Monitoring

At enrollment, potential participants will be appropriately screened for exclusionary psychiatric conditions, medical co-morbidities, and concomitant medications. In addition medical screening will include blood tests including complete blood count (CBC), comprehensive metabolic panel (CMP), urine drug screen (UDS). Subjects with any clinically significant lab abnormalities will be excluded from participation.

Throughout the entire study, suicidal ideation will be assessed during every in-person visit using the C-SSRS and clinical assessment during participant interviews. Significant suicidal ideation is endorsed on items 4 or 5 on the C-SSRS. If the patient screens positive on the C-SSRS at any time during the study, they will undergo a more detailed suicidal risk assessment by study clinician. If they are determined to be at risk of suicide they will be transferred to ED for further Psychiatric evaluation.

During administration, heart rate and BP will be assessed before TRP-8802 capsule administration and at 30, 60, 90, 120, 180, 240, 300, and 360 minutes after capsule administration. Blood pressure and pulse measurements should be preceded by at least 5 minutes of rest for the participant in a quiet setting without distractions (e.g., television, cell phones). If a patient's blood pressure is >200 systolic or >110 diastolic for more than 15 minutes (i.e. 4 consecutive readings) they will be transferred to ED whether or not they are symptomatic.

AEs will be monitored at every study visit. Study staff will also be available throughout the course of the study for emergent AEs. Throughout the administration period, therapists will assess the presence and intensity of participant behaviors, symptoms, and non-verbal cues, which includes questions about the presence/intensity of behaviors, signs, and reported symptoms, such as peacefulness, yawning, nausea/vomiting, quantity of speech, anxiety, sleepiness, crying, restlessness, visual changes, euphoria, and feelings of unreality. They will also complete assessments of mood and safety at the end of the administration sessions.

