## 9.4.4. Exploratory Endpoints (Efficacy)

Exploratory endpoints may be used for possible future investigation(s) and are further described in the SAP.

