# 10.2. Appendix 2: AEs and SAEs: Definitions and Procedures for Recording, Evaluating, Follow-up, and Reporting

#### 10.2.1. Definition of AE

#### **AE Definition**

- An AE is any untoward medical occurrence in a clinical study participant, temporally associated with the use of study intervention, whether or not considered related to the study intervention.
- NOTE: An AE can therefore be any unfavorable and unintended sign (including an abnormal laboratory finding), symptom, or disease (new or exacerbated) temporally associated with the use of study intervention.

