# **Events NOT Meeting the AE Definition**

- Any clinically significant abnormal laboratory findings or other abnormal safety assessments which are associated with the underlying disease, unless judged by the investigator to be more severe than expected for the participant's condition.
- The disease/disorder being studied or expected progression, signs, or symptoms of the disease/disorder being studied, unless more severe than expected for the participant's condition.
- Medical or surgical procedure (e.g., endoscopy, appendectomy): the condition that leads to the procedure is the AE.
- Situations in which an untoward medical occurrence did not occur (social and/or convenience admission to a hospital).
- Anticipated day-to-day fluctuations of pre-existing disease(s) or condition(s) present or detected at the start of the study that do not worsen.

CONFIDENTIAL 62 27 February, 2024

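### Section 8.4 keeps in-session psychedelic reactions off the AE record against an expected level that the protocol does not set, which can leave unchanged or lower, but never raise, the AE results

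*Combined protocol and SAP*

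**What the plan says.** Safety is the primary objective. Section 9.4.2 presents the count and percentage of the Safety Population with an AE, alongside heart rate and blood pressure. For dosing sessions, Section 8.4 adds a recording rule: "manifestations of the psychedelic experience will not be recorded as AEs unless judged by the therapists to exceed the intensity" or the duration of expected reactions.

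Other parts of the protocol bear on that rule:

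- Section 2.2, on earlier psilocybin studies, states that during dose sessions "the most common adverse psychological events included anxiety, negative emotional states and paranoid/delusional thinking".
- Section 10.2.1 defines an AE broadly: "NOTE: An AE can therefore be any unfavorable and unintended sign" (or symptom or disease) associated in time with the intervention. Its list of events that are not AEs covers, for example, "The disease/disorder being studied or expected progression, signs, or symptoms of the disease/disorder being studied". No entry covers acute drug reactions.
- The adverse-event note to Table 2 asks for all AEs and SAEs to be recorded whatever their attribution.
- Section 10.2.3 gives the intensity assessment of each AE to the investigator.
- Sections 5.5 and 10.1.5 pause dosing for Safety Review Committee (SRC) review after one related Grade 3 or 4 AE, or after clinically similar related Grade 2 AEs in 2 participants.

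The same reactions are also captured outside the AE form. Therapists complete the Monitor Rating Form during the session (Section 4.1.4). Participants complete a questionnaire on difficult experiences (Section 8.2.2.3: "The Challenging Experience Questionnaire (CEQ27) assesses challenging experiences and has been frequently used in studies with psychedelics"), which the notes to Table 2 time as follows: "To be performed approximately 7 hours after dosing". Of the therapists, Section 8.5 says: "They will also complete assessments of mood and safety at the end of the administration sessions". Section 10.1.5 has the SRC review all the safety data collected.

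**The concern.** Whether an in-session reaction becomes an AE depends on a prior judgment by the therapists delivering an open-label treatment, against a level that the protocol does not state. The hypothesis in Section 9.1 is that the treatment is safe and well tolerated, and the rule can move the AE results only in the direction that favours it. A reader of the AE table would not see how many reactions were left out or by what standard. The graded stopping rules count AEs, so they inherit the same filter.

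**Working it through.** The plan gives no rate of in-session reactions, no share judged expected and no overlap with other AEs. The only relevant number is the goal of about 10 participants in Section 9.2, chosen by precedent from earlier pilots. There is therefore no figure to reproduce.

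**1. Is the expected level set anywhere?** Section 8.4 names no list, intensity or duration and cites no source. Section 6.8.1 uses the idea of expected challenging experiences again without defining it. Section 2.2 names kinds of reaction but no level. Section 2.3 refers to the Investigator's Brochure for expected adverse events, but Section 8.4 does not make that link.

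**2. Do the passages agree?** Section 2.2 calls certain reactions adverse, and Section 8.4 keeps them off the record by default. Table 2 asks for all AEs. Section 10.2.3 has the investigator rate intensity once an AE exists, while Section 8.4 has the therapists judge intensity to decide whether one exists.

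**3. Direction.** AEs recorded under Section 8.4 are a subset of those that would be recorded without the rule. The denominator, the Safety Population in Table 7, does not depend on what is recorded. So every AE count and percentage, and every count feeding a graded stopping rule, is at most its value without the rule.

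**4. Size for the AE percentage (all rates assumed).** Let q be the share of participants who have in-session psychedelic reactions, all of them left out as expected. Let r be the share with a recorded AE of any other kind.

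- Fall = P(reactions left out and no other AE), which is at most min(q, 1 − r), however the two are associated.
- If the two are independent, fall = q(1 − r).

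| q | r | Ceiling min(q, 1 − r), points | Fall if independent, points |
|---|---|---|---|
| 50% | 90% | 10 | 0.50 × 0.10 = 5 |
| 20% | 80% | 20 | 0.20 × 0.20 = 4 |
| 80% | 80% | 20 | 0.80 × 0.20 = 16 |
| any | 100% | 0 | 0 |
| 37.5% | 30% | 37.5 | 0.375 × 0.70 = 26.25 |

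With 10 participants, one participant is 10 points. The last row takes half the participants as having a reaction and three quarters of those as left out (0.50 × 0.75 = 0.375). The percentage then falls from 1 − 0.70 × 0.50 = 65% to 38.75%. That row needs other AEs in only 30% of participants. Sections 2 and 2.3 describe headache and gastrointestinal effects as common, and Section 8.4.1 collects AEs from Baseline to End of Therapy, so a high r is more plausible. With r at 80% to 100% and q at 20% to 80%, the independent fall runs from 0 to 16 points.

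**5. Graded rules.** A figure for the Grade 2 rule would need the rate of similar related Grade 2 reactions and the share of them judged expected. The documents give neither. The rule filters on intensity and duration, so the share left out probably falls as grade rises. Step 3 gives the direction and nothing further can be derived.

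**The case against.** The strongest case for the plan has four parts.

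- **The rule may simply apply the AE definition.** The note in Section 10.2.1 speaks of signs that are unfavorable and unintended, and a reaction that the treatment is meant to produce may not be unintended. This stands. A reader might infer a flat contradiction between Sections 8.4 and 2.2, but the definition leaves room to reconcile them.
- **The expected level may be set elsewhere.** The Investigator's Brochure, the Psychotherapy Manual or the separate SAP announced in Section 9.4 could state it. This also stands, and a citation in Section 8.4 would answer that part of the point.
- **Nothing is lost.** A reader might infer that in-session distress goes unrecorded. The documents do not support that: therapist ratings, the participant questionnaire and end-of-session assessments exist, and the SRC reviews safety data. What remains is the display. Table 3 makes the form and the questionnaire exploratory, and Section 9.4.4 says only "Exploratory endpoints may be used for possible future investigation(s) and are further described in the SAP". The text reviewed does not commit to showing them with the AE results, though the separate SAP might.
- **Other safeguards do not turn on this judgment in the same way.** Heart rate and blood pressure are measured regardless, Section 8.1.2 makes new suicidal ideation an AE, and the SAE rule and the HPPD trigger in Section 10.1.5 are not based on grade. This stands and limits the reach of the point.

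**Conclusion.** The point holds as a one-way recording filter with an unstated threshold. It can leave unchanged or lower, but cannot raise, the primary AE percentage and the events reaching the graded stopping rules.

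A reader might infer that the AE percentage will be materially understated. The documents do not support that. The fall is confined to participants with no other recorded AE, so it is at most 1 − r: 10 points at an assumed r of 90% and 20 points at 80%. It is probably small on the assumption that most participants have some other AE, such as headache or nausea.

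A reader might also want a figure for how far the Grade 2 rule is weakened. Any such figure would rest wholly on assumed rates, so only the direction is claimed. Meeting a rule leads to a pause and SRC review, after which dosing may resume (Section 5.5).

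Severity is minor to moderate. The direction is certain, but the size is not computable.

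**What to change.** 1. In Section 8.4, state the expected intensity and duration used for recording, or cite the document that does.
2. Record on the AE form in-session reactions of the kinds named in Section 2.2 that reach a pre-stated Monitor Rating Form level, graded by the investigator. The therapists set a yes/no flag for an expected acute psychedelic effect. Reactions they judge beyond expected stay recorded as now, unflagged, so the count without flagged events matches the current rule.
3. Report the AE count and percentage by dose session with and without flagged events, and tabulate the Monitor Rating Form and Challenging Experience Questionnaire results beside them.
4. Reconcile Section 8.4 with the adverse-event note to Table 2, Sections 2.2, 10.2.1 and 10.2.3, and the stopping rules in Sections 5.5 and 10.1.5. The sponsor should state in advance whether flagged events count toward those rules. Which way is for the sponsor to decide.

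The cost is some more AE entries, drawn largely from ratings the therapists already make, and one more table of data already collected. The inclusive AE percentage may look less favourable. The flag remains an open-label judgment, but readers can see it.

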#### 2.3. Benefit/Risk Assessment

Information about the known and expected benefits and risks and reasonably expected adverse events of TRP-8802 may be found in the Tryp-8802 IB.

Due to the psychoactive nature of TRP-8802, it should only be administered in a controlled setting per this clinical protocol. The safety of participants in this study will be enhanced by testing within a "set and setting" protocol as described by Lyons (2018) and by Johnson (2008). By addressing the set (the emotional/cognitive/behavioral state/mindset and expectations of study participants before TRP-8802 exposure) and setting (the physical environment in which the exposure occurs) of the experience, the risk of participants reporting an event which is distressing or injuring themselves can be reduced. Participants will be asked to discuss their session experience thoroughly with the goal of maximizing its therapeutic benefit.

CONFIDENTIAL 19 27 February, 2024

Hallucinogen-persisting perception disorder (HPPD) is a very rare but potentially serious disorder that may occur as a significant adverse effect with the use of psychedelic compounds (mainly lysergic acid diethylamide [LSD]). It is characterized by symptoms such as visual disturbances, derealization, and depersonalization that last from weeks to years after use (Espiard 2005). No cases of HPPD have been reported in volunteers given psilocybin in recent research studies (Griffiths 2016, Studerus 2012, Griffiths 2011). In studies involving cancer patients examining cancer-related anxiety and depression, no cases of HPPD were identified and no patients developed any symptoms of paranoia or anxiety that required pharmacological intervention or anything more than reassurance from session therapists (Studerus 2011).

The risk of experiencing HPPD with 2 doses of TRP-8802 is expected to be very low, and the risk of its occurrence will be reduced by screening participants for potential risk factors such as severe substance use disorder and by excluding people reporting HPPD or other significant adverse events after prior use of hallucinogens. As these symptoms can present even after the duration of the study, participants will be educated about HPPD. If the symptoms were to occur, participants will be instructed to inform the study team immediately (during the study period), and to seek medical care (after the study period), to rule out HPPD.

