# 5.5. Criteria for Temporarily Delaying Enrollment or Administration of Study Intervention

If any of the stopping rules below is met, dosing will pause until the SRC convenes (either routine or ad hoc) to review details of the event and/or additional data. If, after further review of the data, the SRC determines that no stopping rule has been met (e.g., AE determined to be unrelated to the study drug) or that if a stopping rule has been met there is a way to safely continue the trial (e.g., appropriate safety monitoring can be implemented), then dosing may resume. The occurrence of any of the following events will result in a temporary halt of dosing:

- one SAE considered at least possibly related to the study drug
- one Grade 3 or Grade 4 AE considered at least possibly related to the study drug
- clinically similar Grade 2 AEs considered at least possibly related to the study drug in 2 participants

CONFIDENTIAL 33 27 February, 2024

The study may be discontinued at any time by the Institutional Review Board (IRB), the FDA, or other government agencies as part of their duties to ensure that research participants are protected.

CONFIDENTIAL 34 27 February, 2024

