## **6.8.1.** Rescue Medicine

The session therapists are trained to reassure the participants if they experience acute anxiety, agitation, paranoia, or panic. However, in the unlikely event that those symptoms do not respond to reassurance, or if a participant experiences a severe AE outside of the expected challenging experiences associated with psilocybin therapy, one of the session therapists will contact the on-call study physician. The study physician will use their clinical judgment to determine the most appropriate medical intervention.

The study site will supply rescue medication that will be obtained locally. The following rescue medications may be used:

- In the event of a psychiatric emergency, an oral benzodiazepine (e.g., lorazepam) will be available for on-site treatment of panic or anxiety. An oral antipsychotic (e.g., risperidone) will be available for on-site treatment of psychosis or severe agitation.
- In the event of symptomatic hypertension, labetalol or similar will be available for on-site treatment of symptomatic hypertension.
- In the event of new-onset chest pain, the participant will be evaluated in-person by the study physician to determine whether the pain is cardiovascular, musculoskeletal, or reflects acute panic/anxiety. Vital signs and ECG will be monitored (and compared to baseline measurements) for evidence of acute ischemia. Based on physician judgment, sublingual nitroglycerin (available on-site) may be administered as the standard of care for cardiac chest pain while Emergency Medical Services is called to transport the participant to an emergency department. The goal will be to transport an acutely decompensating patient to an emergency department prior to the point where advanced cardiac life support care is required.
- In the event of headache, ibuprofen (400 mg orally) or similar will be available for onsite treatment. If the study physician decides that the use of a rescue medication is warranted, then the study physician or a member of the nursing staff will administer the medication to the participant.

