The date and time of rescue medication administration as well as the name and dosage regimen of the rescue medication must be recorded in the CRF. In the unlikely event that a medical or psychiatric emergency occurs during a drug session and cannot be safely managed by study personnel using reassurance or medication, study staff will contact 911 so that the participant can be transported to an emergency medical department.

In the event that rescue medication is needed, the Investigator and study physicians may use their clinical judgment to implement a future dose modification (Section 6.5) or to discontinue future study intervention (Section 7.1) for that participant.

CONFIDENTIAL 38 27 February, 2024

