#### 8.1.2. Adverse events

Adverse events will be assessed throughout the study as detailed in Section 8.4.

New onset of suicidal ideation will be considered an AE. Suicidal ideation will be assessed during every in-person visit using the C-SSRS and clinical assessment during participant interviews. The C-SSRS was developed by researchers at Columbia University and is widely used in clinical and research settings (https://cssrs.columbia.edu/). Significant suicidal ideation is endorsed on items 4 or 5 on the C-SSRS.

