# 9.4.2. Primary Endpoints (Safety)

The safety of treatment with TRP-8802, which is evaluated by vital signs (HR and BP) and AEs, is the primary endpoint. Vital signs and AEs will be collected from the Baseline (deep

CONFIDENTIAL 56 27 February, 2024

phenotyping) visit until the EOT visit (Day 64) at the time points specified in the SoA (Section 1.3).

Descriptive statistics will be used to present the count and the percentage of participants in the Safety Population who experience an AE.

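### Giving psychiatric rescue medication does not settle whether a dosing-session reaction is an AE, so a medicated reaction judged expected would be missing from the primary AE percentage and the stopping rules

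*Combined protocol and SAP*

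**What the plan says.** Section 8.4 gives the investigator and designees general responsibility for recording AEs. It then makes an exception for dosing sessions. Of reactions that belong to the psychedelic experience it says that they "will not be recorded as AEs unless judged by the therapists to exceed the intensity and/or duration of expected reactions". It sets no threshold for what counts as expected.

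Section 6.8.1 has the therapists call the on-call physician if "those symptoms do not respond to reassurance, or if a participant experiences a severe AE outside of the expected challenging experiences"; Section 8.5 repeats this. The physician chooses the treatment. For psychiatric emergencies, "an oral benzodiazepine (e.g., lorazepam) will be available for on-site treatment of panic or anxiety", and an oral antipsychotic is held for psychosis or severe agitation. When rescue is given, its date and time and "the name and dosage regimen of the rescue medication must be recorded in the CRF". The investigator and study physicians may then change the next dose or stop treatment.

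The primary AE analysis in Section 9.4.2 reads: "Descriptive statistics will be used to present the count and the percentage of participants in the Safety Population who experience an AE". The Section 5.5 stopping rules are all written in terms of AEs or SAEs. One is "one Grade 3 or Grade 4 AE considered at least possibly related to the study drug"; the others are one possibly related SAE, and similar possibly related Grade 2 AEs in two participants.

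**The concern.** Safety is the primary objective, and Section 9.1 hypothesises that the treatment is safe and well tolerated. A reaction that needed a sedative or antipsychotic bears directly on that hypothesis. Yet whether it enters the primary result depends on a judgement by the people delivering an uncontrolled, open-label treatment. An objective marker, the giving of the drug, is already captured on the CRF but is not used to settle the matter.

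The exception comes before everything downstream. The investigator's assessments of intensity and causality in Section 10.2.3 apply to reported AEs. A reaction classed as expected is not an AE, so it receives no grade, and neither the Grade 2 nor the Grade 3/4 rule can be applied to it. A participant could be medicated, lose the second dose and still count as AE-free with the plan followed exactly.

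Elsewhere the protocol fixes the status of psychiatric events by rule. Section 8.1.2 states "New onset of suicidal ideation will be considered an AE", and Section 10.2.2 lists hallucinogen-persisting perception disorder under the SAE definition. There is no such rule for a medicated reaction.

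**Working it through.** **1. Is there an overriding rule?** I looked for text tying psychiatric rescue to AE status.

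- Section 8.4: not recording is the default for psychedelic manifestations; the therapists decide on exceptions.
- Sections 6.8.1 and 8.5: rescue is described, but no AE consequence is stated.
- Section 6.8: any medication is recorded with its reason for use; AE status is not mentioned.
- Sections 6.5 and 7.1: psychosis is named as an adverse event and as a serious adverse event respectively.
- Section 10.2: general AE and SAE definitions; no rule on rescue. An admission could qualify as an SAE.

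Psychosis and admissions are therefore covered. Anxiety, panic or agitation that is medicated but falls short of these is not.

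**2. Effect on the primary percentage.** The plan has no figure to reproduce: Section 9.2 sets about 10 participants by precedent. With n = 10, one participant is 1/10 = 10 points. A true 1/10 (exact 95% interval 0.3% to 44.5%) would be reported as 0/10 (0% to 30.8%) if that participant's only event is unrecorded. A participant with another recorded AE is counted either way.

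**3. How often might a trigger be missed?** Every rate here is assumed; none comes from the documents. Let p be the psychiatric rescue rate per participant and u the share of medicated reactions left unrecorded. Participants are taken as independent and all reactions as possibly related.

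- At least one rescue: 1 − (1 − p)^10.
- At least one unrecorded Grade 3 or higher reaction, assuming 30% of reactions are Grade 3 or higher: 1 − (1 − 0.3pu)^10.
- Missed Grade 2 pair, assuming half of reactions are Grade 2 and clinically similar: P(X ≥ 2) − P(R ≥ 2), with X ~ Bin(10, 0.5p) for true events and R ~ Bin(10, 0.5p(1 − u)) for recorded ones.

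| p | At least one rescue | Unrecorded Grade 3+, u = 0.1 | Unrecorded Grade 3+, u = 0.5 | Missed Grade 2 pair, u = 0.1 | Missed Grade 2 pair, u = 0.5 |
|---|---|---|---|---|---|
| 2% | 18.3% | 0.6% | 3.0% | 0.1% | 0.3% |
| 5% | 40.1% | 1.5% | 7.3% | 0.4% | 1.8% |
| 10% | 65.1% | 3.0% | 14.0% | 1.4% | 6.2% |

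Worked example at p = 10%, u = 0.5: 0.3 × 0.1 × 0.5 = 0.015, and 1 − 0.985^10 = 14.0%. For the pair, 0.0861 − 0.0246 = 0.0615, or 6.2%.

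The second column is only an upper bound on a missed Grade 3/4 pause. The next two columns still overstate it slightly, since another recorded event could trigger the same pause. If most medicated reactions are recorded, the u = 0.1 columns are the relevant ones.

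**The case against.** The strongest reply is that the gap is narrow and the event would be well documented.

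- Section 6.8.1 treats failure of reassurance as improbable and rescue as an emergency measure. A reaction that needs it would ordinarily exceed expected intensity, which is Section 8.4's own test. Section 2.3 reports that in the cited cancer studies "no patients developed any symptoms of paranoia or anxiety that required pharmacological intervention or anything more than reassurance from session therapists". This stands: such reactions should be rare and mostly recorded.
- The drug and the reason for its use are on record (Sections 6.8 and 6.8.1). Therapists rate anxiety and related signs during the session (Section 4.1.4), and the SRC reviews all safety data and may act without a formal trigger (Sections 1.1 and 10.1.5). This also stands, so a reader who infers that the event would be invisible goes too far. But none of these records turns the reaction into an AE or a grade, and the SRC itself includes a study therapist.
- A reader might take the alternatives joined by an or in Section 6.8.1 to mean that reactions unresponsive to reassurance are not AEs. The text does not say so. The second alternative may simply add other severe events as a reason to call the physician. On AE status the sentence is silent.
- Leaving expected drug effects out of the AE count can be reasonable. That is accepted for reactions managed by reassurance alone.
- The Psychotherapy Manual and the later SAP might define what is expected or tabulate rescue use. Neither can be checked here. Section 8.4 as written is a positive rule that stands unless the protocol itself overrides it.

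**Conclusion.** The point holds as a moderate, cheaply closed gap. Under the plan as written, a dosing-session reaction treated with a psychiatric rescue drug can be left out of the AE record if the therapists class it as expected. It is then missing from the primary percentage, ungraded and outside the Section 5.5 triggers.

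Its size rests on a low and unknown frequency. The documents give no rescue rate for this trial, and the cited cancer studies suggest it may be near zero. Per event the effect is large, about 10 points with 10 participants if that participant has no other AE, and less if the Safety Population is larger. Under the assumed rates, the chance of an unrecorded Grade 3 or higher reaction is 0.6% to 3.0% if one in ten medicated reactions goes unrecorded, and 3.0% to 14.0% if half do.

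The documents do not support the stronger inference that medicated reactions will generally be kept out of the AE count, or that a safety pause is likely to be missed. A missed formal pause is possible, not expected.

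**What to change.** In Sections 8.4 and 6.8.1, add: any dosing-session reaction for which psychiatric rescue medication is given is recorded as an AE, graded and assessed for causality by the investigator, and reviewed by the SRC against Section 5.5, whatever the therapists' view of whether it was expected.

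In Section 9.4.2, or in the SAP that Section 9.4 foresees, tabulate rescue use by drug class and dose level (15 mg, 25 mg) beside the AE table.

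The cost is a few more AE records, possibly an extra SRC pause and a slightly less favourable safety profile. No visit or assessment is added. Grading remains a judgement, so the change makes the stopping rules applicable and the SRC review certain, but does not guarantee a halt. Therapist discretion is unchanged for reactions managed by reassurance alone.
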